### 9.6.2. Handling of Missing Data

Element	Reporting Detail
General	
 
Missing data occurs when any requested data are not provided, leading to blank fields on the collection instrument: 
 
These data will be indicated using a “blank” in subject listing displays, unless all data for a specific timepoint are missing in which case the data are excluded from the Table.
 
Answers of “Not applicable” (i.e. within the section ‘Serious Adverse Event of Special Interest [SAE-SI]’) are not considered to be missing data and should be displayed as such.
 
 
 

Data Collection Stopped	
 
For effectiveness endpoints where collection of the underlying data have been stopped as per protocol amendment 3. Data collected for these endpoints prior to their removal from the protocol are available in the previous interim analysis reports.
 

#### 9.6.2.1. Handling of Missing and Partial Dates

Element	Reporting Detail
General	
 
Partial dates will be displayed as captured in subject listing displays
 

Adverse Events Concomitant Medications Medical History Hospitalization	
 
The eCRF allows for the possibility of partial dates (i.e. only month and year) to be recorded for AE start and end dates; that is, the day of the month may be missing. In such a case, the imputation will follow the conventions shown in Section 9.6.2.2. In the event the end date is after to the last contact date, the last contact date (section 9.5.3) will be used.
 
Completely missing start or end dates will remain missing, with no imputation applied. Consequently, time to onset and duration of such events will be missing (where applicable).
 
The recorded partial date will be displayed in listings; so, should not be overwritten.
 

### 9.6.2.2. Imputation Convention for Missing and Partial Dates

Start date	Stop Date	Imputation
Complete date available	Complete date available	Not applicable
Complete date available	Only day is missing	Impute day of stop date with last day of the same month
Complete date available	Month and day are missing	1. Impute stop date with 'Jun30' 2. If (year of start date=year of stop date) then stop date =max (start date + 1, stop date)
Day is missing	Complete date available	Impute the day part of start date with "01" of the same month
Day is missing	Only day is missing	Impute day of start date with '01' and day of stop date with last day of the same month
Day is missing	Month and day are missing	1. Impute day of start date with '01' and 'Jun 30' for day and month of stop date 2. If (year of start date=year of stop date) then stop date =max (start date + 1, stop date)
Day and Month missing	Complete date available	1. Impute start date with 'Jun01' 2. If (year of start date=year of stop date) then start date =min (start date, stop date-1)
Day and Month missing	Only day is missing	1. Impute day of stop date with '30' and 'Jun 01' for day and month of start date 2. If (year of start date=year of stop date) then start date =min (start date, stop date-1)
Day and Month missing	Month and day are missing	Impute start date with 'Jun01' and stop date with 'JUN30'

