7.2 Reporting Adverse Events

7.2.1 Adverse Events of Special Interest

The following adverse events of special interest (AESI) will be collected in this registry:

- Malignancies (excluding non-melanoma skin cancers)
- Mortality
- Opportunistic infections and other infections of interest ([Appendix 1](#))

- Non-melanoma skin cancers (NMSC)
- Selected serious psychiatric events ([Appendix 2](#))
- Serious infections

All AESI identified from enrollment throughout the duration of the study will be recorded on the Adverse Event Case Report Form (AE eCRF). All data fields on the AE eCRF should be completed.

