#### 9.2.1.1. Initial Exposure

This is defined as subjects' exposure arm assignment (Benlysta or Non-Benlysta) at the time of enrollment (Baseline). Due to potential for one or more treatment switching during the follow-up, two different analysis approaches will be used for 'Initial Exposure' strategy; namely, 'ITT' and 'While On Initial Exposure'.

1. ITT approach will use all accrued data during the whole follow-up period irrespective of treatment switching. Subjects entering the study on Benlysta medication will be considered 'Exposed' and those on Non-Benlysta SLE medications are considered 'Unexposed' throughout the study period.

A limitation of the ITT is potential bias from mismatch of events to exposure arm since events occurring after exposure switching are attributed to that Initial Exposure. This will attribute events to Benlysta exposure when subjects are no longer exposed and vice-versa (i.e. Non-Benlysta initial cohort switched to Benlysta). See Section 9.2.1.2 for details of 'As-Exposed' (Time Varying) approach to address this limitation

**Programming Hints for derivation of essential variables needed for computation of incidence and event rates (presented in Section 7.1.5.1) under the ITT approach:**

- Compute individual's subject-years at-risk as:  

$$\frac{[(\text{minimum}(\text{Event Date}, \text{Last Contact Date}^*) - \text{Study Enrollment Date}) + 1]}{365.25}$$

- Compute individual's subject-years of follow-up as:  

$$[(\text{Last Contact Date}^* - \text{Study Enrollment Date}) + 1] / 365.25$$
- Consider events experienced during the whole study period:  

$$\text{Study Enrollment Date} \leq \text{Event Date} \leq \text{Last Contact Date}^*$$
  - For incidence rate calculation only count new cases (i.e. first onset) of the event experienced during the period
  - For events rate calculation count all the events experienced during the period

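### A start date with the day missing is set to the 1st of the month with no floor at enrollment, so an AESI in the enrollment month can be dated before enrollment and drop out of every rate

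*SAP*

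**What the plan says.** SAP 9.6.2.1 states that "The eCRF allows for the possibility of partial dates (i.e. only month and year) to be recorded for AE start and end dates". Its imputation convention also covers concomitant medications, medical history and hospitalizations.

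The table in SAP 9.6.2.2 handles start dates as follows:
- Day missing: "Impute the day part of start date with" 01 of that month. All three rows with only the start day missing do this.
- Day and month missing: 1 June of that year, for example "Impute start date with 'Jun01' and stop date with 'JUN30".
- The only bound on an imputed start is "start date =min (start date, stop date-1", used in some rows. It can move a start earlier, never later.

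End dates do have a bound: "In the event the end date is after to the last contact date, the last contact date (section 9.5.3) will be used". Start dates have no matching lower bound.

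For ITT, SAP 9.2.1.1 says "Consider events experienced during the whole study period" and defines that period as enrollment date to last contact date. While On Initial Exposure has the same lower limit. Under As-Exposed (9.2.1.2) and Ever-Exposed (9.2.1.3) an event must fall inside an exposure period, and the first period starts at enrollment.

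On collection, Protocol 7.2.1 says "All AESI identified from enrollment throughout the duration of the study will be recorded on the Adverse Event Case Report Form".

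**The concern.** The AE form is meant to hold events from enrollment onward, but the imputation can place such an event before enrollment, where no analysis counts it. The primary endpoints are AESI incidences, so a rule that removes events in one direction only deserves correction even if it removes few. Deaths are exposed too, because the programming hints in SAP 9.2.1 assign a death to its analysis period by the onset date of the fatal SAE.

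The same gap touches two other data types. An on-study admission can slip into the six-month baseline window of SAP 5.2. A BENLYSTA start later in the enrollment month can be set to the 1st and meet the baseline medication definition in SAP 9.5.2, which would change the patient's initial exposure group.

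**Working it through.** **Logic.** Take a patient enrolled on 10 September 2016 with an AESI on 22 September 2016.
- Day missing: the imputed start is 1 September, 9 days before enrollment. The event fails the window in every strategy.
- If it were not screened out first, the at-risk formula (event date − enrollment date + 1) would give −9 + 1 = −8 days.
- The result is the same for every day-missing event in the enrollment month unless enrollment was on the 1st.
- For event rates, the event is lost and the follow-up time stays. For incidence rates, the patient also remains at risk until a later event or last contact. Either way the rate can only fall.

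**Planning figures reproduced.** Patient-years are N × (1 − 0.9⁵)/(−ln 0.9) = N × 3.8868. This gives 7,773.5 for 2,000 patients and 3,886.8 for 1,000, matching Protocol 8.2. The half-width for serious infection is 1.96 × √[0.058 × (1/7,773 + 1/3,886)] = 0.927 per 100 patient-years, matching the stated 0.93.

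**Events exposed to the day-missing rule.** The inputs are 3,000 patients, 5.80 serious infections per 100 patient-years (Protocol Table 8-1), and an average of about 15 days left in the enrollment month.
- Expected over the study: 0.058 × (7,773 + 3,886) = 676.
- Expected in the rest of the enrollment month: 3,000 × 15/365.25 × 0.058 = 7.1.
- Lost if 5% to 20% of starts lack the day (assumed): 7.1 × 0.05 = 0.4 to 7.1 × 0.20 = 1.4.
- At the upper end: 1.4/676 = 0.2% of events, or 1.4/11,659 × 100 = 0.012 per 100 patient-years, against the half-width of 0.93.

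**Cross-check by simulation.** 200,000 enrollments were spread over 2013 to 2020, with a constant hazard and five years of follow-up, with and without 10% annual drop-out.

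| Share of day-missing events lost | No floor | Floor at enrollment |
|---|---|---|
| Over 5 years | 0.8% to 1.0% | 0 |
| First 12 months | 4.1% to 4.3% | 0 |

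The direct calculation agrees: 7.1/676 = 1.1%. The loss is concentrated in the 12-month rates that SAP 9.2.1.2 and 9.2.1.3 plan.

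**Rarer endpoints, same assumed shares.**
- Opportunistic infection: 0.00136 × 11,659 = 16 expected. The expected loss is 16 × about 1% × (0.05 to 0.20), or about 0.01 to 0.03.
- Deaths, using the mortality rate as a proxy for fatal-SAE onset: 3,000 × 15/365.25 × 0.0068 = 0.84. Times 0.05 to 0.20, this is 0.04 to 0.17.

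**The 1 June rows.** These matter only for patients enrolled after 1 June: 213/365 = 58% of patients, with on average 213/2 = 106.5 days (0.29 year) left in the year. Exposed serious infections are 3,000 × 0.584 × 0.29 × 0.058, or about 30. If 1% to 2% of AESI dates had only a year (assumed), 0.3 to 0.6 would be lost.

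**The case against.** **Partial dates may be rare for these events.** Serious AESI are to be entered within 24 hours of site awareness (Protocol 7.2.2), all AE form fields should be completed (7.2.1), the data capture system raises queries (11.4), and the final analysis follows database cleaning (SAP 3.2). This stands. The 5% to 20% share is only a range for illustration and may be high.

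**A reader might infer that the 1 June rule removes many AESI.** The documents do not support this. SAP 9.6.2.1 describes partial AE dates as month and year, with the day missing. Year-only rows are needed for the medications and medical history that share the table.

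**A reader might note that one opportunistic infection is 6% of the 16 expected.** That is the weight of a single event, not an expected loss, which is about 0.01 to 0.03.

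**A reader might infer that exposure groups are materially misassigned.** This would need a comparison patient who starts BENLYSTA after Day 4, within the enrollment month, with the day missing. The path exists in the text, but nothing in the documents allows it to be sized.

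**Not every such event is surely on-study.** Protocol 7.2.1 refers to AESI identified from enrollment, and an event with only month and year could have begun earlier that month. This stands and is a cost of any floor.

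**A floor may exist elsewhere.** The AESI work instruction and the mock shells are separate documents that could not be checked. If they contain a floor, SAP 9.6.2.2 need only state it.

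**Conclusion.** The point holds as a minor defect in a stated rule. As written, SAP 9.6.2.2 removes day-missing AESI in the enrollment month from every rate, in one direction only. At the planning rate and an assumed 5% to 20% of starts lacking the day, the loss is about 0.4 to 1.4 of 676 serious infections, mainly affecting the 12-month rates. Year-only AESI dates, which the SAP does not indicate, would add about 0.3 to 0.6. Nothing suggests that the loss differs between cohorts, and it would not change the registry's conclusions. The case for correction is that it is cheap and that a safety registry should not drop events it has recorded.

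**What to change.** Add to SAP 9.6.2.2, before database lock:
- **AESI.** For an AESI on the AE eCRF whose partial start month (or year) is that of enrollment, and whose stop date is not before enrollment, use max(imputed start, enrollment date).
- **Hospitalizations.** For an admission first reported at a follow-up visit, use Day 2 as the floor. A Day 1 floor would fail, because SAP 5.2 counts admissions on the enrollment date as baseline and SAP 5.3 starts on-study admissions at Day 2.
- **Medications.** Apply no blanket floor, because true pre-enrollment starts exist and SAP 5.2 and 9.5.2 count starts on Days 1 to 4 as baseline. For a BENLYSTA start in the enrollment month with the day missing, query the day. Failing that, assign baseline status by whether the record was reported at enrollment or first at follow-up, consistent with the Day 1 to 4 rule.

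The cost is a few lines of text and code, plus a few queries. The downside is that some events that truly began earlier in the enrollment month may be counted as incident. Reporting the number of records changed by the floor, by cohort, would show whether this matters.

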### 9.6.2.3. Handling of Missing Data for Statistical Analysis

Element	Reporting Detail
General	
 
For endpoints not relying on multiple questionnaire items, missing values will not be imputed
 
Data will be analysed only for the time point at which they were collected.
 

SDI Domains	
 
If any item is missing, the total score should be missing. However, if the missing item has previously been score in previous visits, the worst observation can be carried forward for that item.
 
If the SDI is scored inconsistently (a decrease score at subsequent follow-up relative to previous visit has occurred) and the data are unable to be queried and/or corrected, the previous score (before the decrease) will be carried forward at the item level for the SLICC/Damage Index questions, this corresponds to worst observation carried forward (WOCF). These carried forward values at items level will then be used to calculate the total score which will be the value summarized and displayed for reporting.
 

S2K Score	
For the calculation of S2K score, all items will be taken from the completed SLEDAI 2000 CRF page; no imputation will be performed.
 
Scores for any S2K items will be used as observed. Subjects with at least one missing i.e. 'not done' value at baseline assessment will be excluded from the analysis of S2K total score.

## 9.7. Appendix 7: Laboratory Tests

Laboratory Parameter	Units
ANA status	
Anti-dsDNA	
C3	
C4	
CH50	
Lymphocyte differential % / count	
IgA	
IgM	
IgG	
White blood cell (WBC) count	mm 
Neutrophil differential Count	mm 
Thrombocytopenia (<100,000 platelets/10  /L)	
Urinary Casts (Heme-granular or red blood cell casts)	
Hematuria (>5 red blood cells/high power field)	[Units]
Proteinuria (>0.5mg/24 hours)	
Pyuria (>5 white blood cells/high power field)	

## 9.8. Appendix 8: Abbreviations & Trade Marks

### 9.8.1. Abbreviations

Abbreviation	Description
ACR	American College of Rheumatology
ADaM	Analysis Data Model
AE	Adverse Event
AESI	Adverse Event of Special Interest
BMI	Body Mass Index
CDISC	Clinical Data Interchange Standards Consortium
CI	Confidence Interval
CSAP	Clinical Study Activity Plan
CSR	Clinical Study Report
DBL	Database Lock
DCO	Data Cut Off date
eCRF	Electronic Case Record Form
EDC	Electronic Data Capture
EMA	European Medicines Agency
FACIT	Functional Assessment of Chronic Illness Therapy
IA	Interim Analysis
IDSL	Integrated Data Standards Library
IPTW	Inverse Probability of Treatment Weighting
ITT	Intent-To-Treat
MAR	Missing at Random
Max	Maximum
Min	Minimum
NMSC	Non-melanoma skin cancers
PDMP	Protocol Deviation Management Plan
PS	Propensity score
Q1	First Quartile
Q3	Third Quartile
RAP	Reporting & Analysis Plan
PSRHQ	Possible Suicidality-Related History Questionnaire
PSRQ	Possible Suicidality-Related Questionnaire
S2K	SLEDAI 2000
SABLE	Safety And effectiveness of Belimumab in Systemic Lupus Erythematosus Registry
SAC	Statistical Analysis Complete
SAE	Serious Adverse Event
SD	Standard Deviation
SDI	SLICC/ACR Damage Index
SDTM	Study Data Tabulation Model
SERM	Safety Evaluation and Risk Management
SLE	Systemic Lupus Erythematosus

Abbreviation	Description
SLEDAI	Systemic Lupus Erythematosus Disease Activity Index
SLICC	Systemic Lupus International Collaborating Clinics
SMDs	standardized mean differences
TLF	Tables, Listings & Figures
VIF	Variance Inflation Factor

### 9.8.2. Trademarks

Trademarks of the GSK Group of Companies
BENLYSTA

Trademarks not owned by the GSK Group of Companies
MedDRA
SAS® version 9.4 or higher (SAS Institute, Cary, NC, USA)
Domino 5.9.1

## 9.9. Appendix 9: Treatment Propensity Score Models Covariates

**Table 4: Treatment Propensity Score Models Covariates**

Variables	Categories/Units	Key covariates*
Year of entry in the study	2013/2014 2015/2016 2017/2018 2019/2020	
Age at baseline	Years	Yes
Sex	Female Male	Yes
BMI	Underweight (<18.5) Normal (18.5 - <25) Overweight (25 - <30) Obese (30 - <40) Extremely obese (>=40)	
Race	Black White Asian Other	Yes
Ethnicity	Hispanic/Latino Not Hispanic/Latino	
Region	US/Canada Europe Other	Yes
Baseline Clinical SLEDAI 2000 score	Score	Yes
Baseline SDI	Score	
SLE duration since diagnosis	Years	
Used corticosteroids for SLE in the past six months	Yes No	Yes
Cardiovascular risk factors	Yes No	
Allergic reactions	Yes No	
Interstitial lung disease	Yes No	
Chronic Obstructive Pulmonary Disease (COPD)	Yes No	
Opportunistic Infection	Yes No	

Variables	Categories/Units	Key covariates*
Any other infection	Yes No	
Autoimmune disorders	Yes No	
Hypogammaglobulinaemia	Yes No	
Cancer	Yes No	
Non-Melanoma Skin Cancer (NMSC)	Yes No	
Family history of cancer	Yes No	
End stage renal failure	Yes No	
Depression and/or anxiety disorder	Yes No	
Suicidal ideation and/or suicidal depression and/or suicidal behavior	Yes No	
Attempted suicide	Yes No	
Dialysis	Yes No	
Transplant	Yes No	
Splenectomy	Yes No	

Treatment propensity score models covariates are collected at baseline.

\* Key covariates will be included in PS models. They are selected based on clinical judgment. If during building the PS model, there is a need to simplify the model specification, retention of key variables will be given priority. Any model simplification involving removal of these key covariates, will require further discussions and alignment with study team prior to implementation.

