6.1 Study Enrollment Evaluations

The following data will be collected at enrollment (baseline). Data collection for enrollment may be carried out over more than one clinical evaluation visit.

1. Written informed consent (including consent for the use and disclosure of research-related health information).
2. Demographics (eg, age, gender, race/ethnicity (where allowed by local regulation), smoking history, alcohol use)
3. Medical history (including SLE history). Note: To collect additional important information on potential suicidality-related events, should any of the psychiatric events marked with an asterisk in [Appendix 2](#) be present at enrollment, the investigator should complete the Possible Suicidality-Related History Questionnaire (PSRHQ) eCRF (see [Appendix 3](#)).
4. Potential Confounders for Malignancies and/or Infections List (refer to [Appendix 7](#)).
5. Obtain historical and current SLE medications (immunosuppressants, antimalarials, corticosteroids and biologics). The name of the each SLE medication and start and stop dates will be recorded. In addition, for corticosteroids, the prescribed dose will be recorded. If the patient is receiving BENLYSTA, the date of first dose, and route of administration (IV or SC) will be recorded as well as name of the other SLE medications the patient was receiving at the time BENLYSTA therapy was initiated.
6. SLEDAI 2000 (see [Appendix 6](#)). To complete SLEDAI 2000, data from the following laboratory tests if available: Hematology (WBC, platelets), complement (C3, C4), anti-dsDNA, routine urinalysis, and spot urine for macroscopic/microscopic/proteinuria assessments. Note: Laboratory values should not be attributed on the SLEDAI 2000 unless laboratory values were obtained within 30 days of enrollment otherwise the laboratory values will be noted as not done.
7. SLICC/ACR Damage Index ([Appendix 5](#)).
8. Hospitalizations occurring in the previous 6 months.

9. Confirm patient meets study eligibility criteria.

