Additional safety analysis will be performed comparing BENLYSTA treatment initiators with patients from the comparison cohort that start or switch an immunosuppressant and that have comparable background medication and treatment history. Subgroup analysis will be performed that will include but not be limited to analysis of patients with positive anti-dsDNA and low complement at baseline, patients with SLEDAI 2000 score at baseline (< 10 vs ≥ 10), SDI (0 vs ≥ 1), steroid use (yes vs no; ≤ 7.5 mg/day vs > 7.5 mg/day), immunosuppressant use (yes vs no; mycophenolate vs immunosuppressant other than mycophenolate), region (US/Canada vs Europe vs other), and race (black race vs other). Safety analyses will be adjusted for potential confounding factors ([Appendix 7](#)) through propensity score methods or other appropriate statistical methods. No new analyses for changing between BENLYSTA formulation or

stratifying by BENLYSTA formulation are planned. Further details of the safety analyses will be described in the statistical analysis plan.

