Appendix 7 Potential Confounders for Malignancies and/or Infections List

- **Demographic and other general characteristics**
 - Age
 - Gender
 - Weight
 - Height
 - Race/ethnicity
 - Smoking history
 - Family history of cancer – first degree relatives & grandparents
 - Alcohol history
 - Female only:
 - Parity
 - Hormonal status

- **SLE disease profile**
 - Age at diagnosis
 - Organ involvement (SLEDAI 2000 Domains)
 - Disease Severity (SLEDAI 2000)
 - Organ Damage (SDI)
 - ANA status
 - Anti-dsDNA status
 - Quantitative Immunoglobulins (IgG, IgA, IgM)
 - Complement levels (C3/C4)
 - Total white blood cell count
 - Neutrophil differential %
 - Lymphocyte differential %

- **SLE treatment**
 - Name and duration of current SLE medications: including anti-malarials, biologics, steroids, and immunosuppressants at baseline
 - In addition, for steroids add dose

- **Co-morbidities**
 - ESRD/dialysis
 - Hepatitis B
 - Hepatitis C
 - HIV
 - Sjogren's Syndrome (Secondary)
 - Neutropenia
 - Post-transplant (any transplant)
 - Diabetes
 - Splenectomy

GlaxoSmithKline group of companies

- Chronic lung disease
 - Known immunoglobulin deficiencies
 - Tuberculosis (latent or active)
 - History of cancer (including NMSC)
 - History of serious infection
-
- **Vaccinations**
 - BCG
 - Pneumococcal
 - Influenza vaccine
 - Human papillomavirus (HPV)
 - Hepatitis
 - Varicella zoster
 - Any live vaccine received 30 days prior to enrollment

Signature Page for 116543 TMF-14148167 v2.0

Reason for signing: Approved	Name: PPD Role: A Date of signature: 25-May-2022 14:05:04 GMT+0000
------------------------------	--

Reason for signing: Approved	Name: PPD Role: A Date of signature: 25-May-2022 14:10:27 GMT+0000
------------------------------	--

Signature Page for TMF-14148167 v2.0

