### 7.3.1.4. Missing Data on Covariates

Considering the background of the study, missingness is known for the baseline confounders. Among variables listed in Table 4, Body Mass index (BMI), Race, Ethnicity, SDI and SLEDAI 2000 score are reported with missing values. The rules below will apply:

- The missing data for individual variables will be coded into a “missing” category for categorical variables to allow all subjects to be used in the analysis; for continuous measures, missing data will be set to a fixed value (i.e. median) and an indicator variable will be added in the model.
- However, in the case of very few missing cases ( $<10$ ):
  - The modal category will be assumed for categorical variables.
  - The indicator variable will be omitted from the model for continuous variables
- Specific case of baseline SLEDAI 2000 (S2K composite score):

The Assessments of SLEDAI 2000 score consist of 24 individual items (see section 9.5.5) in which signs and symptoms, laboratory tests, and physician’s assessment for each of 9 organ systems are given a weighted score and summed if present (marked ‘Yes’).

  - A “Clinical SLEDAI 2000 score” (CS2K) will be computed considering all items except “Low Complement” and “Increased DNA Binding”. The CS2K is computed based on the remaining 22 items, with either “absent” or “not done” being regarded as 0.
  - A corresponding variable “total not-done points” calculating the sum of not done weights is also included in the model. "Total not done points" = 0 for subjects who were assessed for all items. "Total not done points" = 18 for subjects with maximum (6) not done items. The variable’s inclusion is to allow the model to differentiate between subjects who have scored x points/101 available compared to subjects who have score x points/83 available, or anywhere in between.
- If the SLEDAI 2000 form is completely missing, then median CS2K (based on subjects who answered  $>0$  questions) and median “total not done points” will be assumed, and an indicator variable will be added in the model.

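### SAP Table 4 narrows the protocol's list of confounders without giving a reason, and no listed output shows whether the omitted factors are balanced after weighting

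*SAP*

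**What the plan says.** Protocol 8.3.2 states: "Safety analyses will be adjusted for potential confounding factors". It cites Appendix 7 as the list, allows propensity scores or another suitable method, and leaves details to the SAP. Appendix 7 includes smoking history, anti-dsDNA, C3/C4 and "Name and duration of current SLE medications: including anti-malarials, biologics, steroids, and immunosuppressants at baseline", followed by "In addition, for steroids add dose". The same section plans a comparison of Benlysta initiators with comparators who start or switch an immunosuppressant and "that have comparable background medication and treatment history".

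SAP 7.3 is the only confounding-adjusted analysis in the SAP. Its propensity model uses the 29 variables of Table 4 (Appendix 9). Steroids enter as "Used corticosteroids for SLE in the past six months", Yes or No. The nearest row to smoking is "Cardiovascular risk factors", whose components are not defined. Disease activity enters as a clinical SLEDAI score without low complement and DNA binding: "The CS2K is computed based on the remaining 22 items" (7.3.1.4).

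The weighted rates receive no further covariate adjustment (7.3.3). Balance is assessed and displayed for the model variables only (7.3.1.2.2, 7.3.2, Table 53.020). The weighted outcome tables are 54.010 and 54.020, neither split by cohort. SAP 2.1.1 declares no change of approach apart from separating two infection categories.

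**The concern.** A factor left out of the propensity model is balanced by weighting only so far as it is correlated with factors that are in it. The protocol treats several of the omitted factors as important. Section 1.1 links corticosteroids, and complement abnormalities in active disease, to infection. Section 1.3 names background treatment as a confounder. Section 8.3.2 sets subgroups on anti-dsDNA with low complement and on steroid dose.

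Crude imbalance will be visible in Tables 7.000 (tobacco), 14.100 and 14.200 (SLE medications), 15.000 (steroids) and 19.000 (laboratory values), all in the Eligible population. None of these is weighted. The model could therefore meet its own balance criterion while an omitted risk factor for infection stays unbalanced, and the report would not show it. The initiator comparison, which is the least exposed to prevalent-user bias, has only unweighted tables listed (for example 24.112 and 24.122).

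**Working it through.** **1. Line-by-line comparison.**

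| Protocol Appendix 7 item | SAP Table 4 |
|---|---|
| Steroid dose | Steroid use Yes/No |
| Antimalarials | No term |
| Anti-dsDNA | No term; SLEDAI item dropped |
| Complement C3/C4 | No term; SLEDAI item dropped |
| Smoking history | Not named; possibly inside the cardiovascular composite |

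Partial control comes from clinical SLEDAI, prior infection, COPD, cancer history and hypogammaglobulinaemia. Baseline steroid dose category, anti-dsDNA and low complement are already descriptive covariates in SAP 5.6.1.

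**2. Check that serology is outside the severity score.** The SLEDAI weights in SAP 9.5.5 sum to 8×8 + 6×4 + 7×2 + 3×1 = 105. Removing the two serology items (2 + 2) gives 101. The SAP's maximum of 18 not-done points matches four urine items and two blood counts (4×4 + 2×1 = 18), and 101 − 18 = 83. Both 101 and 83 agree with 7.3.1.4.

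**3. The plan's own precision.** Person-years: 2,000 × (1 − 0.9^5)/(−ln 0.9) = 7,773.5, and half of that, 3,886.8, for 1,000 patients. These match 7,773 and 3,886. Serious-infection half-width: 1.96 × √(0.058 × (1/7,773 + 1/3,886)) = 0.927 per 100 patient-years, matching 0.93. For deaths the same formula gives 0.318, matching 0.32 in Table 8-1.

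**4. How large could the bias be?** The documents give no input, so everything in this step is an assumption: one omitted binary factor, no true drug effect, prevalence p0 = 35% in comparators, residual imbalance of 5, 10 or 15 points after weighting, and an outcome rate ratio RR of 1.5, 2 or 3. Bias factor = (1 + p1(RR − 1))/(1 + p0(RR − 1)).

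| RR | +5 points | +10 points | +15 points |
|---|---|---|---|
| 1.5 | 1.021 | 1.043 | 1.064 |
| 2 | 1.037 | 1.074 | 1.111 |
| 3 | 1.059 | 1.118 | 1.176 |

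With the imbalance reversed, the extremes are (1 + 0.30×0.5)/(1 + 0.35×0.5) = 0.979 and (1 + 0.20×2)/(1 + 0.35×2) = 0.82. With p0 = 20% the upward range is 1.023 to 1.214; with p0 = 50% it is 1.020 to 1.150.

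**5. Against the planned half-widths (Table 8-1).** Ratio = (bias factor − 1) × rate / half-width.

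- Serious infection (5.80, ±0.93): 0.13 to 0.37 at 5 points, 0.27 to 0.73 at 10, 0.40 to 1.10 at 15.
- Deaths (0.68, ±0.32): 0.05 to 0.38.
- Malignancy excluding NMSC (0.226, ±0.19): at most 0.21.
- Opportunistic infection (0.136, ±0.14): at most 0.17.

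If weighting inflates the variance by 1.2 to 1.5 (assumption), the largest serious-infection ratio falls to about 1.0 and 0.90.

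**6. Would a balance table catch it?** SMD = difference/√((p0(1 − p0) + p1(1 − p1))/2). At p0 = 35% this is 0.103, 0.205 and 0.307 for 5, 10 and 15 points. The 0.1 guide in SAP 7.3.1.2.2, applied to the omitted factors, would flag an imbalance from about 5 points upwards.

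**The case against.** The strongest reply is that no promise has been broken. Appendix 7 is a list of potential confounders for malignancies and infections and serves as a data-collection list. It is not a model specification. SAP 7.3.1.2.1 prespecifies covariates chosen by medical experts. This stands, and it is why a reader who infers a protocol breach goes further than the documents do. What remains is that the SAP gives no reason for any omission while declaring no change of approach.

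Some omissions are also defensible. In current users, steroid dose, antimalarial use and serology at enrolment may already reflect treatment. Serology depends on "data from the following laboratory tests if available" (protocol 6.1). Every eligible comparator is on an immunosuppressant (SAP 4.1), so a Yes/No term for that would strain positivity. This too stands: the omissions do not show that the primary model is wrong.

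Smoking may be inside "Cardiovascular risk factors", so a claim that it is uncontrolled is not supported.

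A reader might also infer that no weighted initiator analysis is planned. The table list shows none, but the mock shells are a separate file and the figure in 7.3.4 is not shown. The cohort wording is mixed: 5.6.2 says separate analyses will be done, 3.2 and 7.1.5.1 say they may be, and Section 7 makes separation a default that can be overridden. The protocol does not name weighting for this comparison. It is a mismatch to reconcile.

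Finally, the SAP reports arm-specific rates with intervals, compared descriptively, so the bias factors above apply to a ratio the reader would form. They illustrate scale and estimate nothing.

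**Conclusion.** The point holds as an unexplained narrowing of the adjustment set, with no listed output to show whether it matters. The covariate comparison is certain from the text. The statement about balance rests on SAP 7.3.2 and the table titles, since the mock shells could not be checked.

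Neither the direction nor the size of any bias can be derived from the documents. On the assumptions above, it approaches the planned precision only for serious infection, and only with a strong risk factor and a large residual imbalance. For deaths, malignancy and opportunistic infection it stays well inside the planned half-width. The change should be made before the final analysis, because the weighted tables are the SAP's only adjusted result. Confidence is moderate.

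**What to change.** (a) Beside Table 53.020, report SMDs before and after weighting for steroid dose category, antimalarial use, anti-dsDNA, low complement and smoking, read against 0.1. Keep them for reporting only, outside the stop rule in 7.3.1. This is the cheapest step and worth doing alone. It needs some programming outside the CAUSALTRT output.

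(b) Define the cardiovascular composite. If it does not include smoking, add smoking to Table 4.

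(c) Run one labelled sensitivity propensity model that adds antimalarial use, baseline steroid dose category, anti-dsDNA and low complement, with the 7.3.1.4 missing-data rule. Show it beside the primary model, which otherwise stays as it is. State in SAP 2.1.1 which of these factors are left out of the primary model and why.

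(d) Add Treatment Initiator versions of Tables 54.010 and 54.020 with the propensity score refitted in that cohort, and reconcile 5.6.2 with 3.2 and 7.1.5.1. Initiators may have started up to 61 days before enrolment, so the concern about baseline values reflecting treatment is smaller there but not absent.

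The costs are extra programming, more variable weights, possible bias if serology is often missing (the documents give no completeness figure), and wider intervals in initiators. If initiators supply 30% to 50% of person-years (assumption), the serious-infection half-width rises from 0.93 to 0.927/√0.5 = 1.31 up to 0.927/√0.3 = 1.69 per 100 patient-years. With a weighting variance inflation of 1.2 to 1.5 (assumption), it becomes 1.31×√1.2 = 1.44 up to 1.69×√1.5 = 2.07.
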